## 2. OBJECTIVES

### **Primary Objective:**

- To verify the concordance between stress cMRI and conventional technique (angiography, eco-stress) in evaluation of pediatric patient with suspected coronary artery disease.

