### **Secondary Objectives:**

- To optimize the scan protocol and the sequence parameters
- To investigate the clinical compliance of stress induced cardiac MRI in pediatric patients
- To test the ability of stress cMRI to visualize coronary arteries morphological irregularities, the corresponding wall motion abnormalities and perfusion - viability features
- To find a correlation between cMRI data and clinical status and other diagnostic tools, parameters and variables.
- To demonstrate the advantage of stress cMRI over cMRI in evaluation of pediatric patient with

suspected coronary artery disease.

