### 4. STUDY PROCEDURES

The study population will be recruited, over a period of approximately 24 months, from children attending the ward and the outpatient clinics of the cardiologic paediatric unit, in accordance with the following inclusion criteria.

4.1 Inclusion Criteria are: Between 8 and 18 years-old patients symptomatic and non, with suspected or previously diagnosed coronary arteries disease: Coronary artery re-implantation after arterial switch, ALCAPA Syndrome, other anomalies of origin or pathway, replacement of aortic valve with pulmonary autograft (Ross procedure), Kawasaki disease, primary dilatative cardiomyopathy, coronary atresia, familial Hypercholesterolemia, bicuspid aortic valve, chest pain, exertional dyspnea of suspected coronary artery nature, coronary artery fistula.

4.2 Exclusion criteria are: General contraindication to MRI (non MRI compatible device: vascular clips, foreign bodies, coronary and peripheral artery stents, aortic stent grafts, prosthetic heart valves and annuloplasty rings, cardiac occluder devices, vena cava filters and embolisation coils, haemodynamic monitoring and temporary pacing devices, haemodynamic support devices, permanent cardiac pacemakers and implantable cardioverter-defibrillators, retained transvenous pacemaker and defibrillator leads, cochlear implants, claustrophobia, pregnancy and postpartum), contraindication to contrast agent (renal insufficiency, hypersensitivity to the Dotarem active substance or to any of the excipients:), contraindication to stress agent (hypersensitivity to Dobutamine active substance or to any of the excipients; severe arterial hypertension ( $\geq 220/120$  mmHg), unstable angina pectoris, significant aortic stenosis, complex cardiac arrhythmias including uncontrolled atrial fibrillation, hypertrophic obstructive cardiomyopathy, myocarditis, endocarditis, pericarditis, uncontrolled congestive heart failure, previous manifestations of hypersensitivity to dobutamine, refuse to join the protocol and relative off-label procedures.

A total number of 15 patients fitting the above criteria is the target of our study.

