### Cardiac MRI PROTOCOL

MRI scanner: Philips Achieva 1.5 T. 32 Channel Cardiac Coil.

A. Scout sequences

B. SSFP 2-Chamber left, SSFP 2-Chamber right, SSFP 4-Chamber

C. DOBUTAMINE in increments of 10  $\mu\text{g}/\text{kg}$  body weight/minute every 3 minutes starting at 10  $\mu\text{g}/\text{kg}$  body weight/minute until target heart rate [ $85\% \times (220 - \text{age})$ ] reached.

- D. Dotarem injection (0,1 mmol/kg, 2 ml/sec) when the target heart rate is reached
- E. Stress perfusion Images in Short Axis and 4-Chamber
- F. Cine Short Axis from base to apex for volumetric analysis
- G. Late Gadolinium enhancement
- H. Rest perfusion Images in Short Axis and 4-Chamber
- I. 3D Navigated SSFP in transversal plane
- L. Aorta and Pulmonary flow

Patients were queried about their symptoms before and after Dobutamine administration. Sublingual nitroglycerine and iv metoprolol are available for severe and persistent chest pain during or after the exam.

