#### 4.4 STATISTICAL CONSIDERATIONS

Data will be described as means, standard deviation (SD) and medians with a range for continuous variables, while absolute and relative frequencies will be used for categorical variables.

Categorical data will be compared by chi-square test or by Fisher's exact test in case of expected frequencies  $<5$ . Comparisons of quantitative variables will be performed by Student's t test for paired data or Wilcoxon test. Concordance between MRI- and traditional test will be determined by the Kappa statistical method as described by Landis and Koch, and  $\kappa$  will be interpreted as follows:  $\kappa$  value of 0 indicates poor agreement;  $\kappa$  value of 0.01–0.20, slight agreement;  $\kappa$  value of 0.21–0.40, fair agreement;  $\kappa$  value of 0.41–0.60, moderate agreement;  $\kappa$  value of 0.61–0.80, substantial agreement; and  $\kappa$  value of 0.81–1; almost perfect. p-value less than 0.05 will be considered statistically significant, and all p-values will be based upon two tailed tests. Statistical analysis will be performed using SPSS for Windows (SPSS Inc, Chicago, Illinois USA).

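### For a continuous quantity measured by both cMRI and another exam, section 4.4 names only a paired t or Wilcoxon test, which does not measure agreement

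*Protocol*

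**What the plan says.** The primary objective (section 2) is concordance between stress cMRI and conventional technique, and the primary endpoint is agreement of results with current practice. One secondary objective is: "To find a correlation between cMRI data and clinical status and other diagnostic tools, parameters and variables".

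Section 4.4 sets out the methods:
- Categorical data: chi-square or Fisher's exact test.
- Continuous data: means, SDs and medians with range for description. For inference: "Comparisons of quantitative variables will be performed by Student's t test for paired data or Wilcoxon test".
- Concordance: "Concordance between MRI- and traditional test will be determined by the Kappa statistical method as described by Landis and Koch".
- Testing: "p-value less than 0.05 will be considered statistically significant", and "all p-values will be based upon two tailed tests".

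On size, section 4 says: "A total number of 15 patients fitting the above criteria is the target of our study".

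Several exams yield quantities that can be continuous. The cMRI protocol in section 4.3 includes "Cine Short Axis from base to apex for volumetric analysis" and acquires aortic and pulmonary flow. Under Other Exams, the echo covers left chamber function and pulmonary artery diameters, flow and greatest velocity. Angiography covers pulmonary diameters and pressures, and the exercise test gives oxygen uptake and heart rate as percent of predicted.

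**The concern.** The study asks whether one method can stand in for others, yet the only inferential method named for continuous variables is a test of difference. A paired t or Wilcoxon test asks whether the mean or median difference is zero. It does not describe how far the two readings lie apart in an individual child, which is what matters if one exam is to replace another. Scatter enters the test only as noise: around a given bias, a larger scatter makes that bias harder to detect.

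At stake is the reading of any continuous comparison between modalities. Section 1 says the aim, if results support it, is to replace the current procedure with stress cMRI. With a paired p-value as the only named inferential result, a non-significant finding in 15 children could be taken as support when it says little. Conversely, two methods that track each other closely but differ by a small constant offset could be reported as significantly different, with nothing to show that the offset is small.

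**Working it through.** **Inputs from the protocol.** n = 15 (section 4); two-sided alpha 0.05 and a paired test (section 4.4). The protocol gives no SD, bias, correlation or agreement threshold, and no derivation of 15, so there is no stated figure to reproduce.

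**Assumptions, not in the documents.** Each method has a between-child SD of 7 units, the mean difference is 3 units, and the correlation r between methods is varied. Differences are normal.

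**Step 1: what the test can detect.** With standardised bias d = bias / SD of the differences, the paired t statistic has 14 degrees of freedom and noncentrality d × √15. The critical value is 2.145.
- d = 0.5: noncentrality 0.5 × 3.873 = 1.94; power 0.438, so the bias is missed 56% of the time.
- 80% power requires d = 0.778.

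**Step 2: effect of scatter at a fixed bias.** SD of the differences = 7 × √(2(1 − r)); half-width of the limits of agreement = 1.96 × that SD. Bias is held at 3.

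| r | SD of differences | Limits of agreement | d | P(p ≥ 0.05) |
|---|---|---|---|---|
| 0.9 | 3.13 | 3 ± 6.1 | 0.96 | 6.9% |
| 0.5 | 7.00 | 3 ± 13.7 | 0.43 | 66.0% |
| 0 | 9.90 | 3 ± 19.4 | 0.30 | 80.6% |

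Only r changes between rows. Unrelated methods give a non-significant result far more often than closely related ones with the same offset. A second set of assumptions (SD 10, bias 5) shows the same pattern: about 0% at r = 0.95, 18.8% at 0.8, 56.2% at 0.5 and 75.2% at 0. A Wilcoxon simulation in that setting (4,000 runs each) gives 0%, 21.5%, 58.8% and 76.4%.

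**Step 3: where that pattern stops.**
- Zero bias: P(p ≥ 0.05) = 95% whatever the scatter, because that is 1 − alpha. Tightly agreeing and wholly unrelated methods then give the same result.
- Fixed SD of differences of 10, bias growing 0, 2.5, 5, 10: P(p ≥ 0.05) = 95%, 85.3%, 56.2%, 5.1%. When disagreement takes the form of bias, the test does respond to it.

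**Step 4: precision of the alternative at n = 15.** CI half-width of one limit of agreement = 2.145 × √(1/15 + 1.96²/28) = 2.145 × 0.4515 = 0.97 SD of the differences. For a correlation (Fisher z, Pearson), the half-width on the z scale is 1.96/√12 = 0.566. An observed 0.5 has a 95% CI of −0.02 to 0.81, and an observed 0.7 has 0.29 to 0.89.

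**The case against.** The strongest reply is that section 4.4 does name an agreement statistic. The sentence on kappa covers concordance between MRI and the traditional tests, so the primary endpoint has a suitable type of measure when results are categorical. That stands, and it confines the point to continuous quantities.

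The sentence on paired tests also has a proper use. Section 4.3 defines baseline and peak heart rate and blood pressure, and a paired t or Wilcoxon test is right for that within-child change. This stands too.

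A reader might infer that the plan will treat a non-significant paired test as proof of agreement. The document does not say so: it sets no pass rule on that test and does not link it to concordance. A reader might also infer that the test always favours methods that agree worse. It does not. That holds only for added scatter around a fixed non-zero bias.

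The protocol also does not list pairs of identical continuous measures. Percent-predicted oxygen uptake has no stated cMRI counterpart, no comparator exam is said to report volumes, and echo left chamber function is not said to be numeric. The point therefore depends on overlapping quantities being recorded as numbers, which is plausible for function, pulmonary flow and diameters.

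Finally, a statistical analysis plan that is not shown could name a correlation coefficient or a test by clinical status, and the term Wilcoxon test could include the rank-sum form. Those absences alone are no finding. What is left is that 4.4 does not stay silent on quantitative comparisons; it assigns them a method that does not suit comparisons between modalities.

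**Conclusion.** The point holds for one class of analysis: the same continuous quantity measured by cMRI and by another exam in the same child. There the only inferential method named tests mean or median shift, does not measure agreement, and at n = 15 is weak even for that shift (44% power at 0.5 SD of the differences, 80% only at 0.78 SD). With the assumed SD of 7 and bias of 3, the chance of a non-significant result rises from about 7% to 81% as the correlation falls from 0.9 to 0. Those percentages depend on the assumed SD and bias; the power figures do not, since they are in units of the SD of the differences.

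The categorical primary analysis by kappa is not affected. The documents do not support saying that the protocol will misread a non-significant test, only that it gives no better measure for continuous data and no warning against that reading. This is a worthwhile and inexpensive improvement, not a flaw that undermines the primary endpoint.

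**What to change.** Amend section 4.4 as follows:
- For the same quantity measured by two methods in the same child, make the Bland-Altman mean difference and 95% limits of agreement, each with a 95% CI, the main analysis. List the quantities to which this applies.
- State that a non-significant paired test is not evidence of agreement.
- Keep the paired t or Wilcoxon test for within-child change, such as baseline to peak heart rate and blood pressure.
- For the secondary correlation objective, report Spearman correlation with a 95% CI.

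This changes wording only and needs no new data, exams or patients. The downside is presentational: with 15 children each limit of agreement carries a CI of about ±0.97 SD of the differences, and correlations will be similarly imprecise, so the results will look less favourable than a non-significant p-value. That imprecision is a true feature of a 15-patient pilot and is better shown.

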## 1. BACKGROUND

Transposition of the great arteries, the most common cyanotic congenital heart lesion found in neonates, accounts for 5%–7% of congenital cardiac malformations.

Arterial switch surgery is now the treatment of choice for transposition of the great arteries. In this procedure, the aorta and main pulmonary artery are transected, switched, and re-anastomosed to the correct ventricle. The coronary arteries and a small portion of aortic sinus are excised when the aorta is transected and are re-implanted once the aorta is connected to the left ventricular outflow tract.

Most complications and mortality occur within the first year of life, and are secondary to myocardial ischemia or infarction associated with relocation of the coronary arteries at surgery. Nonetheless, follow-up studies have revealed a significant prevalence (7-8%) of coronary stenosis, occlusions and late death in an otherwise symptom-free patient population.

Other pathologic condition affecting coronary arteries during pediatric age, with a lower incidence than transposition of coronary arteries, are: Kawasaki disease, primary dilatative cardiomyopathy of undetermined nature, ALCAPA syndrome and other coronary artery anomalies of origin and pathway, coronary fistula, coronary atresia, familial hypercholesterolemia, bicuspid aortic valve, chest pain or dispnea related to exercise of suspected coronary nature.

Following current practice, pediatric patients affected by or with suspected coronary artery disease undergo to Exercise Test, Eco stress and Coronary Angiography. While coronary angiography (CA) is considered the gold standard for detection of coronary lesions necessitating possible interventions, CA is a invasive and x-ray exposing technique which cannot be included in regular follow-up in asymptomatic children.

Cardiovascular Magnetic Resonance imaging (cMRI) provides both morphologic and functional information that can be decisive in the treatment of neonates and infants with congenital heart disease. Thanks to its non-invasiveness and lack of ionizing radiation, cMRI is now becoming a major imaging tool in pediatric congenital heart disease.

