**Primary Endpoint:**

- Agreement of results between stress cMRI and the current practice constituted by Exercise test, Stress Cardiac Ultrasound and Invasive Angiography.

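### Kappa is the only agreement statistic named for the primary endpoint; with 15 children it can be undefined, or 0 and labelled *poor*, despite near-complete agreement

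*Protocol*

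**What the plan says.** The primary endpoint (Protocol, section 2) is "Agreement of results between stress cMRI and the current practice constituted by Exercise test, Stress Cardiac Ultrasound and Invasive Angiography". For its analysis, section 4.4 states: "Concordance between MRI- and traditional test will be determined by the Kappa statistical method". The same paragraph fixes a verbal scale. A "value of 0 indicates poor agreement", and positive values rise in bands to *almost perfect* at 0.81–1. There is no band below 0 and no mention of a kappa that cannot be computed. No other agreement measure is named; the section's general rule is that categorical variables are described by counts and percentages.

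Section 4 sets the size: "A total number of 15 patients fitting the above criteria is the target of our study". No expected kappa, precision or positive rate accompanies it. The only lesion rate in the protocol is in section 1, after the description of the arterial switch operation: "follow-up studies have revealed a significant prevalence (7-8%) of coronary stenosis, occlusions and late death in an otherwise symptom-free patient population". Eligibility is wider (section 4.1): "Between 8 and 18 years-old patients symptomatic and non, with suspected or previously diagnosed coronary arteries disease".

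**The concern.** Kappa divides the excess of observed over chance agreement by one minus chance agreement. When positives are few, chance agreement is close to 1, and the statistic either has no value or turns on where a single positive child falls. At n = 15 that is a practical possibility. The primary result could then have no value, or carry the label *poor*, when 14 or 15 of 15 children have the same result on both tests. Section 1 says the aim is to replace the current work-up with stress cMRI if the results support it, so a label that does not track agreement is a weak basis for that decision.

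**Working it through.** **Inputs from the protocol.** n = 15 (section 4); kappa and its scale (section 4.4); 7–8% as the only rate quoted (section 1). The protocol gives no figure for the behaviour of kappa, so there is none to reproduce.

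**Assumptions.** One binary result per child on each side; the protocol does not fix the unit. Sensitivity and specificity (Se/Sp) of cMRI against the reference of 0.95/0.99 and 0.90/0.95. Prevalence other than 7–8% is an assumed range.

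**Step 1: kappa from the table.** Let a = both positive, b = cMRI positive only, c = reference positive only, d = both negative. Then

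- Po = (a + d)/15
- Pe = [(a+b)(a+c) + (c+d)(b+d)]/15²
- κ = (Po − Pe)/(1 − Pe)

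| a, b, c, d | Po | Pe | κ | Label in 4.4 |
|---|---|---|---|---|
| 0, 0, 0, 15 | 1 | 1 | 0/0 | none |
| 0, 1, 0, 14 | 14/15 = 0.933 | (1·0 + 14·15)/225 = 0.933 | 0.00 | poor |
| 1, 1, 0, 13 | 0.933 | (2·1 + 13·14)/225 = 0.818 | 0.63 | substantial |
| 7, 1, 0, 7 | 0.933 | (8·7 + 7·8)/225 = 0.498 | 0.87 | almost perfect |
| 0, 1, 1, 13 | 13/15 = 0.867 | (1·1 + 14·14)/225 = 0.876 | −0.07 | none |

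The three middle rows all have 14 of 15 children in agreement. None of these rows needs an assumed prevalence.

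**Step 2: frequency under perfect agreement.** Kappa is undefined when no child (or every child) is positive: P = (1−p)^15 + p^15. The second term is negligible at low p.

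- 7%: 0.93^15 = 33.7%, with 15 × 0.07 = 1.05 positives expected
- 8%: 0.92^15 = 28.6%, with 1.2 positives expected
- 10%: 20.6%
- 15%: 8.7%
- 20%: 3.5%
- 30%: 0.5%

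Under perfect agreement none of these cases is a zero.

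**Step 3: frequency under high but imperfect agreement.** All 2×2 tables with n = 15 were enumerated, with multinomial cell probabilities p·Se, (1−p)(1−Sp), p(1−Se) and (1−p)Sp.

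| Prevalence | Se/Sp | Undefined | Exactly 0 | Negative | Undefined or ≤0 |
|---|---|---|---|---|---|
| 7% | 0.95/0.99 | 29.0% | 6.4% | 0.3% | 35.6% |
| 7% | 0.90/0.95 | 15.6% | 20.0% | 2.0% | 37.7% |
| 8% | 0.95/0.99 | 24.6% | 5.7% | 0.3% | 30.6% |
| 8% | 0.90/0.95 | 13.3% | 17.3% | 2.0% | 32.6% |
| 10% | 0.90/0.95 | 9.5% | 12.9% | 1.9% | 24.3% |
| 20% | 0.90/0.95 | 1.6% | 2.7% | 0.8% | 5.1% |
| 30% | 0.90/0.95 | 0.2% | 0.5% | 0.2% | 0.9% |

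(Totals are summed before rounding.) At 7–8% with 0.90/0.95, kappa is undefined or ≤0 while at least 13 of 15 children agree in 31–36% of trials. Most of these failures therefore do not reflect real disagreement.

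**The case against.** The strongest objection is to the prevalence. A reader might infer that the protocol expects 7–8% positives and that the primary analysis therefore fails one time in three. The documents do not support that. The figure combines stenosis, occlusion and late death in symptom-free patients, while the trial also admits symptomatic and already diagnosed children with many coronary conditions. The reference is a composite of three tests, so its positive rate may exceed a lesion rate. This stands: 7–8% is a low-prevalence scenario, and at 20% or more the failure is uncommon. Nothing in the eligibility rules excludes a low rate, however, since asymptomatic and merely suspected cases are admitted without quota.

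A reader might also infer that every failed kappa would be reported as *poor*. That is not so. Under perfect agreement the failed value is undefined and unlabelled; *poor* attaches only to an exact zero, which needs at least one disagreement.

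Stress ultrasound is reported by 17 segments (section 4.3, Other exams), so a per-segment kappa with up to 15 × 17 = 255 clustered units is conceivable. The protocol gives no segment result for the exercise test or angiography, so one result per child is the more natural reading of the composite endpoint, but it remains an assumption.

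Finally, this is a pilot with no success threshold on kappa. Counts and percentages would probably be tabulated anyway, and the handling of an inestimable statistic is often left to an analysis plan not shown here. That lowers the severity. It does not remove the point, because the protocol itself fixes the statistic and the label for 0.

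**Conclusion.** The point holds as a conditional weakness that should be fixed. It does not show that the trial cannot answer its question. Regardless of prevalence, the sole named agreement statistic and its fixed scale can give 14/15 agreement any label from *poor* to *almost perfect*, and they leave negative values unclassified.

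The frequency is conditional on one binary result per child and on the positive rate. If positives were as rare as 7–8%, kappa would be undefined in 29–34% of trials under perfect agreement. It would be undefined or ≤0 in about 31–38% under the assumed accuracies, of which exact zeros, the only cases read as *poor*, account for about 6–20% of trials. Across perfect agreement and the assumed accuracies, the undefined-or-≤0 rate is about 21–24% at 10% prevalence, 4–5% at 20% and under 1% at 30%. The protocol gives no basis for choosing among these rates.

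**What to change.** In section 4.4:

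- Report the 2×2 table with overall, positive and negative percent agreement and exact 95% confidence intervals as the primary read-out, beside kappa.
- Report kappa as not estimable, without a verbal label, when either test has no positives or no negatives.
- Extend the lowest class of the scale to all values ≤0.

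A further coefficient less sensitive to prevalence (AC1 or PABAK) is optional.

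The cost is a few sentences and a few lines of analysis, with no new data. The downside is that the headline is no longer a single verbal label. The change also cannot create information. With 15 joint negatives, overall agreement would be 15/15 with an exact lower limit of 0.025^(1/15) = 78%, but positive agreement would have no denominator and should be reported as such.
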